### **8.6.4 Medical History**

Medical history data will be coded using Medical Dictionary for Regulatory Activities (MedDRA) and summarized by MedDRA System Organ Class (SOC), Preferred Term, and treatment group. The data will also be listed, including the verbatim investigator description of the relevant medical condition, the coded terms (SOC, Preferred Term), start date, end date, and whether or not the condition is ongoing.

---

A separate coding listing will be created with all the distinct levels of SOC, Preferred Terms, and the verbatim investigator description reported in the study. Sorting will be alphabetically by SOC, Preferred Term, and then verbatim description.

### **8.6.5 Prior and Concomitant Medications**

All medications will be coded using the World Health Organization Drug Dictionary. All prior and concomitant medications will be listed and summarized separately by Anatomical Therapeutic Chemical class 3 (ATC 3), Preferred Term, and treatment group. The use of medications will be summarized separately by study period. Additionally, a coding listing of unique medications and their corresponding coding will be presented.

### **8.6.6 Antipruritic Medication**

Prior and concomitant antipruritic medications will be summarized separately by study period; summaries will be presented by ingredient rather than by ATC codes.

## **8.7 Efficacy Analysis**

### **8.7.1 Primary Efficacy Endpoint**

The primary efficacy endpoint is defined as the proportion of patients achieving  $\geq 3$ -point improvement from baseline with respect to the weekly mean of the daily 24-hour Worst Itching Intensity NRS at Week 12 (Days 79 to 85) of the Double-blind Treatment Period.

The weekly mean of the 24-hour Worst Itching Intensity NRS score will be defined as the sum of the daily Worst Itching Intensity NRS scores reported during a specific week during the Double-blind Treatment Period (eg, Days 2 to 8, Days 9 to 15, Days 16 to 22, ... Days 79 to 85) divided by the number of days with nonmissing scores for that week. If the daily worst itching score is missing for  $>3$  days during a specific week, the corresponding weekly mean worst itching score will be set to missing. The baseline score will be defined as the average of the daily 24-hour Worst Itching Intensity NRS scores collected over the Run-in Period, including pre-randomization assessments collected on Day 1.

In the primary efficacy analysis, missing NRS data will be imputed using a multiple imputation (MI) approach, assuming that patients who discontinue double-blind treatment early would have similar Worst Itching Intensity NRS scores as other patients in their respective treatment arm that have complete data:

- Intermittent missing NRS scores will first be imputed using the Markov Chain Monte Carlo (MCMC) method implemented with the SAS MI procedure, which is appropriate for non-monotonic missing data.
- NRS scores missing after patients discontinue study drug early will then be multiply imputed with the SAS MI procedure using a method appropriate for

monotone missingness (eg, regression statement). Details on the MI procedure can be found in [Appendix 14.6](#).

- The proportion of patients who have an improvement from baseline with respect to the weekly mean of the daily 24-hour Worst Itching Intensity NRS score  $\geq 3$  points will be calculated for each imputed dataset. Differences between CR845 0.5 mcg/kg and placebo with respect to the primary endpoint will be compared using a logistic regression model containing terms for treatment group, baseline NRS score, use of prior anti-itch medication, presence of specific medical conditions, and country/region.
- Results of the logistic regression on the multiply imputed data sets will be summarized by the SAS MIANALYZE procedure.

The final p-value will be calculated using the Cui, Hung, Wang (CHW) procedure where the z-score is a weighted average of the z-score at the interim and the z-score observed for data collected after the interim, following the formula below.

$$Z_{\text{final}} = Z_{\text{interim}} * \sqrt{(n/N)} + Z_{\text{post-interim}} * \sqrt{(1 - n/N)}$$

where n is the number of patients at the interim and N is the initial number of patients planned (300).

Sensitivity analyses of the primary efficacy endpoint will be conducted to evaluate the robustness of study results under different assumptions and imputation algorithms. For each of these sensitivity analyses, the final p-value will be calculated based on the CHW procedure, using the formula specified above.

- **Sensitivity 1:** Early discontinuations as nonresponders

Patients who discontinue study drug early will be considered nonresponders. The imputed data will be analyzed using a logistic regression model similar to the primary analysis.

- **Sensitivity 2:** Multiple imputation; missing not at random (MNAR)

This sensitivity analysis is an implementation of a pattern mixture model that draws from different populations based on the reason for withdrawal.

- Intermittent missing NRS scores will first be imputed using the MCMC method with the SAS MI procedure, which is appropriate for non-monotonic missing data.
- For patients who discontinued study drug due to adverse events, NRS scores missing after discontinuation will be imputed using the distribution of the baseline value of all patients' daily worst itching score assuming a trimmed normal (from 5 to 10).
- For patients who discontinue due to reasons other than adverse event, missing NRS scores after patients discontinue study drug early will be multiply

imputed using multiple calls of the SAS MI procedure using data from patients within the same treatment group that have complete data at that time. The proportion of patients who have an improvement from baseline with respect to the weekly mean of the daily 24-hour Worst Itching Intensity NRS score  $\geq 3$  points will be calculated for each imputed dataset

- Similar to the primary analysis, results of the logistic regression on the multiply imputed data sets will be summarized by the SAS MIANALYZE procedure.
- **Sensitivity 3:** Tipping point analysis  
Multiple imputation with mixed missing data mechanisms (MNAR for a missing data pattern and MAR for others) will be used to assess the robustness of the MAR assumption. This sensitivity analysis is to investigate the departure from MAR assumption by progressively decreasing the treatment differences with respect to the NRS scores over the missing visits in active treatment group until conclusion from the primary analysis is overturned. The MI procedure includes the following steps:
  - Uses MCMC methodology from PROC MI by treatment group to impute the intermittent missing data to a monotone missing pattern
  - Uses a standard MAR-based MI approach from PROC MI to impute data from monotone missing data
  - For patients in the active treatment group, shift parameter from PROC MI will be progressively applied to impute the missing data, until the p-value  $> 0.05$

To evaluate the potential impact of the IA on the properties of statistical inference at the end of the trial, the primary and sensitivity analyses of the primary endpoint will also be presented separately for the sample of patients enrolled into the study after the IA.

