## 1.0 Protocol Synopsis

STUDY TITLE	A Multicenter, Double-blind, Randomized, Placebo-controlled Study to Evaluate the Safety and Efficacy of Intravenous CR845 in Hemodialysis Patients with Moderate-to-Severe Pruritus, with a 52-Week Open-label Extension
PROTOCOL NUMBER	CR845-CLIN3103
EUDRACT NUMBER	2018-001930-17
PHASE OF DEVELOPMENT	3
INVESTIGATIONAL PRODUCT	CR845 Solution (for clinical trial use only)
NAME OF ACTIVE INGREDIENT	CR845
ROUTE OF ADMINISTRATION	Intravenous (IV)
STUDY CENTERS	Approximately 95 US and non-US sites
OBJECTIVES	
Primary Objective
 
 
To evaluate the efficacy of IV CR845 at a dose of 0.5 mcg/kg compared to placebo in reducing the intensity of itch in hemodialysis patients with moderate-to-severe pruritus.
 
 
Secondary Objectives
 
 
To evaluate the efficacy of IV CR845 at a dose of 0.5 mcg/kg compared to placebo in improving itch-related quality-of-life measures in hemodialysis patients with moderate-to-severe pruritus.
 
To evaluate the safety of IV CR845 at a dose of 0.5 mcg/kg in hemodialysis patients with moderate-to-severe pruritus.
 

NUMBER OF PATIENTS	The planned sample size is 350 (175 per treatment group) male and female hemodialysis patients with moderate-to-severe pruritus. The sample size may be increased to 500 patients (250 per treatment group) based on the results of a planned interim assessment conducted when approximately 50% of the planned 350 patients have been randomized and have either completed the 12-week Treatment Period or have discontinued study drug early.
STUDY POPULATION	
Inclusion Criteria:
 
To be eligible for inclusion into the Double-blind Phase of the study, a patient must meet the following criteria:
 
 
Willing and able to provide written informed consent prior to participating in this study;
 

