### 8.2 Determination of Sample Size

The planned sample size for this study is 350 (175 per treatment group) male and female hemodialysis patients with chronic moderate-to-severe pruritus (mean baseline 24-hour Worst Itching Intensity NRS score  $\geq 5$ ), randomized at approximately 95 clinical sites. The sample size may be increased to 500 patients (250 per treatment group) based on the results of a planned unblinded interim assessment conducted when approximately 50% of the planned 350 first patients have been randomized and have either completed the 12-week Double-blind Treatment Period or have discontinued from double-blind treatment early. The planned interim assessment will be conducted by an Independent Data Monitoring Committee (IDMC). Details related to the sample size re-estimation are included in [Section 8.4.1](#).

The sample size calculation is based on results of a completed Phase 2 double-blind, placebo-controlled study (CR845-CLIN2101) of CR845 in hemodialysis patients who had moderate-to-severe pruritus. In this study, approximately 30% of patients randomized to the placebo group reported  $\geq 3$ -point improvement from baseline with respect to the 24-hour Worst Itching Intensity NRS at the end of treatment (Week 8). The proportion of patients who received CR845 and reported a similar improvement in itch scores ranged from approximately 60% to 45% (ie, 30% to 15% difference from

placebo), depending on the dose of active study drug (0.5 mcg/kg, 1.0 mcg/kg, 1.5 mcg/kg).

Given a sample size of 350 patients (175 per treatment group) and assuming a true response rate of 30% for the placebo group and a true response rate of 50% for the CR845 group (defining response as an improvement from baseline  $\geq 3$  points with respect to the Worst Itching Intensity NRS at Week 12), a 2-sided continuity corrected Chi-square will have 96% power to detect a treatment difference. The power of this test statistic would be  $\geq 84\%$  for differences from placebo as low as 0.16 (Table 4).

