## **8.4 Interim Analysis**

### **8.4.1 Sample Size Re-estimation**

An unblinded interim analysis for sample size re-estimation will be conducted when approximately 50% of the first 350 patients have been randomized and have either completed the 12-week Double-blind Treatment Period or have discontinued from double-blind treatment early. The planned interim assessment will be conducted by an IDMC. An unblinded statistician who will not be part of the study team will provide results of the interim analysis to the IDMC members. Members of the IDMC will not participate in the Data Safety Monitoring Board (DSMB) and will not be members of the study team. During the interim assessment, the study team will remain blinded to the data; however, the IDMC will receive unblinded summary results to implement the decision rule for sample size re-estimation. The IDMC will only communicate the decision to either keep the original sample size or to increase it; no other results will be provided to blinded staff. The DSMB will be made aware of the decision, but not given the results that were the basis of the decision.

[REDACTED]

[REDACTED]

[REDACTED]

[REDACTED]

[REDACTED]

[REDACTED]

[REDACTED]

[REDACTED]

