Should a sample size increase occur, the above process will be implemented completely independently among subjects contributing the interim results and those following the interim analysis.

For the tipping point analysis, a shift parameter will be applied to only subjects in the active group, running from 0 to 5 points in 0.25-point increments or until the conclusions of the analysis “tip” and the results are no longer significant. This analysis will not be performed should the initial primary results fail to achieve significance.

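### The CHW formula for the primary p-value sets the initial planned size at 300, but the trial is planned for 350

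*Protocol*

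**What the plan says.** Section 8.7.1 obtains the final primary p-value from Z_final = Z_interim × sqrt(n/N) + Z_post-interim × sqrt(1 - n/N), and explains the symbols as follows: "where n is the number of patients at the interim and N is the initial number of patients planned (300".

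The same section extends the rule to the supporting analyses: "For each of these sensitivity analyses, the final p-value will be calculated based on the CHW procedure, using the formula specified above".

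The initial size is stated differently everywhere else that is readable:

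- Synopsis: "The planned sample size is 350 (175 per treatment group) male and female hemodialysis patients with moderate-to-severe pruritus".
- Section 8.2: "The planned sample size for this study is 350 (175 per treatment group", and Table 4 is headed with 175 per arm.
- Section 8.4.1 times the interim from the same total: "conducted when approximately 50% of the first 350 patients have been randomized".

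The only other planned total is the re-estimated maximum of 500.

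Section 14.6 writes the stage-wise analysis for one case only: "Should a sample size increase occur, the above process will be implemented completely independently among subjects contributing the interim results" and those enrolled after it. Section 8.7.1 attaches no such condition to the CHW formula.

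**The concern.** The definition of N contradicts itself. Its words point to the initial planned size, which is 350; its figure is 300. The two readings give different stage weights and so different p-values from the same data.

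This matters because of what the formula decides. It produces the p-value on which the study is called positive, and under section 8.7.3 a non-significant primary result makes every secondary test non-inferential. CHW controls the type I error because its weights are settled before the post-interim data are seen. A sentence that supports two sets of weights leaves that choice open.

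**Working it through.** **Inputs.** Initial size 350, or 175 per arm (synopsis, 8.2, Table 4). Interim at about 50% of 350 (8.4.1), so n = 175; this is an assumption, because the actual n may differ somewhat. Maximum size 500 (8.2). Response rates 30% v 50% at the design alternative and 30% v 45% as the smallest difference in Table 4. Two-sided 5% test (8.7.3).

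**Which total the design rests on.** Continuity-corrected power is Φ((d - 1/m - 1.96 × se0)/se1). Here m is patients per arm, d the difference in response rates, se0 the pooled and se1 the unpooled standard error.

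| Placebo 30% v CR845 | 50% | 48% | 46% | 45% |
|---|---|---|---|---|
| Table 4 | 96% | 92% | 84% | 79% |
| m = 175 (total 350) | 96.3% | 92.0% | 84.8% | 79.9% |
| m = 150 (total 300) | 93.2% | 87.2% | 78.4% | 73.0% |

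Table 4 is reproduced to within a point at 350 and not at 300. Table 5 (134, 164, 204, 230, 262) is reproduced exactly as per-arm sizes.

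**Weights at n = 175.**

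- N = 300: sqrt(175/300) = 0.7638 and sqrt(125/300) = 0.6455.
- N = 350: sqrt(175/350) = 0.7071 for both stages.

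For any n, the interim weight with N = 300 is sqrt(350/300) = 1.080 times the one with N = 350. The looseness of "approximately" 50% therefore does not remove the difference.

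**Type I error.** The squared weights sum to n/N + (1 - n/N) = 1 for either N, so either version, fixed in advance, has a 5% level. The correlation between the two versions of Z_final is 0.7638 × 0.7071 + 0.6455 × 0.7071 = 0.9965. If the more favourable version could be chosen after unblinding, the bivariate normal with that correlation gives a two-sided error of about 5.4%.

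**Opposite verdicts.** N = 300 gives the larger Z_final when 0.0567 × z1 > 0.0616 × z2, that is, when the interim z exceeds about 1.09 times the post-interim z.

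- z1 = 1.0, z2 = 1.8. N = 300: 0.7638 × 1.0 + 0.6455 × 1.8 = 1.926, p = 0.054. N = 350: 0.7071 × 2.8 = 1.980, p = 0.048.
- z1 = 2.0, z2 = 0.75. N = 300: 0.7638 × 2.0 + 0.6455 × 0.75 = 2.012, p = 0.044. N = 350: 0.7071 × 2.75 = 1.945, p = 0.052.

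**Power and disagreement.** Power = Φ(w1 × d1 + w2 × d2 - 1.96), where d1 and d2 are the stage drifts of the difference in proportions (unpooled variance, no continuity correction). Stage 1 has 87.5 per arm; stage 2 has 87.5 per arm (total 350) or 162.5 per arm (total 500). For example, at 30% v 45% and a total of 500, d1 = 2.074 and d2 = 2.827, so the means of Z_final are 3.409 (N = 300) and 3.466 (N = 350). Disagreement on significance comes from the bivariate normal above.

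| Rates | Final size | Power, N = 300 | Power, N = 350 | Verdicts differ |
|---|---|---|---|---|
| 30% v 50% | 350 | 97.3% | 97.4% | 0.4% |
| 30% v 50% | 500 | 99.5% | 99.6% | 0.1% |
| 30% v 45% | 350 | 83.2% | 83.5% | 1.7% |
| 30% v 45% | 500 | 92.6% | 93.4% | 1.1% |

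**The case against.** The strongest reply is that this is a slip in one number with little effect. The words already tell the reader which total is meant, the 5% level holds either way, and the power loss is at most about 0.75 points. At the design alternative the verdict changes in no more than 0.4% of trials, and the worked examples come from a narrow band around 0.05. All of that is correct and limits the severity.

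Three further points have some force.

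- Section 8.1 gives the SAP precedence, and parts of 8.4.1 are blacked out, so the constant may be right where it will be applied. That cannot be seen here; the SAP may equally have copied the 300.
- The rows for 500 patients treat every trial as enlarged. In the trial, enlargement depends on the interim result through a rule that is not visible. The actual analysis is also logistic regression after multiple imputation. The figures are therefore illustrative and are not operating characteristics of the adaptive design.
- The gap in 14.6 is a separate drafting matter. With N = 350, n = 175 and no enlargement, the stage-wise and single analyses agree asymptotically, so it adds nothing to the severity.

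None of this explains the 300 or reconciles it with the rest of the protocol.

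**Conclusion.** The concern holds: the figure is wrong as written. No readable text in the protocol supports 300 as the initial planned size, and the protocol's own power table rests on 350. The interim weight becomes 0.764 instead of 0.707, assuming n = 175. The statistical cost is small: no loss of type I error control if one value is fixed beforehand, a power loss of about 0.1 to 0.75 points, and a different verdict in 0.1% to 1.7% of trials under the simplified calculation. It should be fixed because the constant sits in the formula for the decisive p-value and its sensitivity analyses, and the correct choice must not remain open once the data are unblinded.

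**What to change.** Before unblinding, replace 300 by 350 in the definition of N in section 8.7.1, and confirm that the SAP carries the same value. This is the direct correction: the interim weight stays sqrt(n/350) and follows the actual interim n. Prespecifying both weights as sqrt(0.5) is a legitimate alternative, but it equals the corrected formula only when n is exactly 175. If that is preferred, it should replace the formula, so that only one rule stands.

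As a separate minor edit, add one sentence to 14.6 saying how its stage-wise analysis, written only for an enlarged trial, fits the unconditional CHW rule in 8.7.1.

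The cost is one number and one sentence. Design, data collection and sample size do not change, and there is no statistical downside.

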## 14.6 Statistical Appendix

This appendix provides further details related to the treatment of missing data for the primary and sensitivity analyses of the primary endpoint.

For multiple imputations and other instances where random seeds are required, the values used (in order) are:

8392857  
2985729  
1843255  
9086284  
5547484  
8017456  
9597295  
2252256  
4821871  
9852467  
5126715  
3232132  
9841654  
3645284  
1587345

Note that not all seeds may be required in programming the multiple imputations. If additional seeds are needed, they will be chosen by adding 1 to each of the values above, again using them in order.

The number of imputations for the multiple imputations will be 20.

For the primary analysis, a multi-stage process will be applied:

Stage 1: Subjects will have their 11-point NRS scores imputed. First, using all visits, intermittent missing data will be imputed using the Markov Chain Monte Carlo (MCMC) method implemented with the SAS MI procedure; data imputed following subject discontinuation via this process will be censored out of the resulting dataset so that only intermittent missing data is imputed via this method. Second, monotone missing data will be imputed following subject discontinuation using SAS proc MI. For each stage, MI will be performed within treatment group with covariates for baseline NRS score, use of prior anti-itch medication, and presence of select medical conditions. Should convergence issues occur due to small cell size for the one or both of the categorical covariates at either stage, the appropriate covariate(s) will be removed from the model.

Stage 2: Using the resulting complete datasets, the change from baseline with respect to the 11-point NRS will be calculated; patients will be categorized as responder if they have a 3-point (or greater) improvement over baseline. Week 12 values will serve as the primary timepoint. The 20 MI runs will be analyzed independently using a logistic

---

model and the results combined using SAS proc MIANALYZE. Logistic model covariates will include treatment, baseline NRS score, use of prior anti-itch medication, and presence of select medical conditions. As with the MI, should convergence issues occur due to small cell sizes, the appropriate categorical covariate(s) will be dropped as necessary.

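### Sensitivity 1 and Sensitivity 2 leave patients still on study drug but without a Week 12 itch score imputed under MAR, and Sensitivity 3 does not say clearly whether its shift reaches them

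*Protocol*

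**What the plan says.** All of this is in Protocol section 8.7.1 unless noted.

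- **Missing weekly mean.** When more than 3 daily scores are absent in a week, "the corresponding weekly mean worst itching score will be set to missing". The rule does not depend on whether the patient is still on drug.
- **Primary analysis.** "Intermittent missing NRS scores will first be imputed using the Markov Chain Monte Carlo (MCMC) method implemented with the SAS MI procedure". A second, monotone step then handles scores missing after study drug is stopped. For the primary analysis, Appendix 14.6 removes the MCMC values that follow discontinuation "so that only intermittent missing data is imputed via this method". A gap that does not follow discontinuation therefore stays in the MCMC step, which is run within treatment group.
- **Sensitivity 1.** "Patients who discontinue study drug early will be considered nonresponders. The imputed data will be analyzed" with a logistic model like that of the primary analysis.
- **Sensitivity 2.** "Intermittent missing NRS scores will first be imputed using the MCMC method with the SAS MI procedure". Only adverse-event discontinuers are drawn from a different (baseline) distribution. Other discontinuers are imputed from patients in the same arm.
- **Sensitivity 3.** MCMC is used by arm "to impute the intermittent missing data to a monotone missing pattern", the monotone remainder is imputed under MAR, and a shift is applied to missing data in the active arm. The text says one pattern is missing not at random (MNAR) and the others MAR, but does not name that pattern. Appendix 14.6 adds that the shift runs from 0 to 5 points, in the active group only.

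**The concern.** Stopping study drug and stopping the diary are different events here. Staff give the drug at dialysis (section 6.4.1), while the itch score comes from a daily worksheet that is filled in at home on non-dialysis days (section 6.5.3.1). A patient can therefore be fully dosed and have no Week 12 score.

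The sensitivity analyses are meant to show whether the result survives other assumptions about missing data. If patients whose itch has not improved are more likely to let the diary lapse, within-arm MAR imputation gives them too favourable a response rate. If this happens more often on CR845, the treatment difference is overstated. Sensitivity 1 and Sensitivity 2 could not reveal that, because neither changes how these patients are handled. The nonresponder analysis is usually read as the conservative one, so its agreement with the primary result would carry more weight than it should for this group.

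**Working it through.** **1. Can a fully dosed patient lack a Week 12 score?** Week 12 is Days 79 to 85 (section 8.7.1). Dialysis visits in that window fall on Days 80, 82 and 85 (Table 2), which leaves Days 79, 81, 83 and 84 at home. Three unit scores and no home scores means 4 missing days. Since 4 > 3, the weekly mean is missing. One home score would bring the count to 3 and rescue the mean. The gap is therefore possible with full attendance, but it needs all four home scores to be absent, or some unit scores to be absent as well.

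**2. How each analysis treats that patient.**

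| Analysis | Who departs from MAR | On-drug patient, no Week 12 mean |
|---|---|---|
| Primary | nobody | MCMC within arm (MAR) |
| Sensitivity 1 | study drug discontinuers | stays as imputed (MAR) |
| Sensitivity 2 | adverse-event discontinuers | MCMC (MAR) |
| Sensitivity 3, plain wording | missing data in the CR845 arm | a gap running to Week 12 is already monotone, so it takes the shift |
| Sensitivity 3, Appendix 14.6 split carried over | CR845 scores missing after discontinuation | filled by MCMC before the shift (MAR) |

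In the placebo arm such gaps stay MAR under Sensitivity 3 on either reading, because the shift is applied to the active arm only.

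**3. The plan's own power figure.** Inputs from section 8.2 and Table 4: n = 175 per arm, 50% vs 30%, two-sided 5%, continuity-corrected chi-square. With d the difference in rates:

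- Continuity-adjusted size: n' = (n − 1/d)² / n = (175 − 5)² / 175 = 165.1.
- z = [d√n' − 1.96√(2p̄(1 − p̄))] / √(p₁(1 − p₁) + p₂(1 − p₂)) = (2.570 − 1.358) / 0.678 = 1.79.
- Power = 96.3%, against 96% stated.

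The full Table 4 row gives 96.3%, 92.0%, 84.8% and 79.9%, against 96%, 92%, 84% and 79%. Table 5 reproduces exactly (134, 164, 204, 230, 262 per arm). No stated figure is in dispute.

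**4. Illustration of what the wider nonresponder rule would show.** Let m be the share of an arm that is on drug without a Week 12 mean. The protocol gives no value, so m is assumed. If MAR imputation returns the planning rate p, counting these patients as nonresponders gives p(1 − m). Each row uses the power formula in step 3.

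| Assumed m, CR845 / placebo | Rates | Difference (points) | Odds ratio | Power |
|---|---|---|---|---|
| 0 / 0 | 50.0% vs 30.0% | 20.0 | 2.33 | 96.3% |
| 5% / 5% | 47.5% vs 28.5% | 19.0 | 2.27 | 94.8% |
| 10% / 10% | 45.0% vs 27.0% | 18.0 | 2.21 | 92.8% |
| 10% / 5% | 45.0% vs 28.5% | 16.5 | 2.05 | 87.4% |

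For the 10% / 5% row: 0.50 × 0.90 = 0.450 and 0.30 × 0.95 = 0.285. Sensitivity 1 as written would show the first row whatever the value of m, as far as this source of missingness goes.

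**The case against.** **Sensitivity 3 does test these patients.** A reader might infer that all three sensitivity analyses leave this group under MAR, so that the assumption is never tested. The documents do not support that. Sensitivity 3 runs MCMC only until the pattern is monotone. Week 12 is the last week, so a gap that runs to the end is already monotone. By the written order it passes to the monotone step and takes the shift in the CR845 arm. Nothing in section 8.7.1 or Appendix 14.6 limits the shift to discontinuers. This objection stands. What remains is an ambiguity: the MNAR pattern is unnamed, and the only explicit split between intermittent and post-discontinuation data is the one written for the primary analysis.

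**The group may be small.** A patient who completes the three unit worksheets needs only one of four home scores. The larger power losses also require unequal missingness between arms, for which the protocol gives no evidence. This stands as a limit on size. It does not remove the gap, since unequal missingness is what a sensitivity analysis should probe.

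**The Per-Protocol analysis removes persistent diary stoppers.** Section 8.5 excludes patients with weekly scores missing in at least 25% of study weeks, which is 3 of 12. A patient missing only Weeks 11 and 12 (2/12 = 17%) stays in. Excluding patients is also not a test of MAR.

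**Sensitivity 1 does what its title says, and the SAP governs missing data.** Both are true: the title refers to early discontinuations, and section 8.1 gives the SAP primacy. There is no contradiction in the text, and treating on-drug diary gaps as MAR is a common choice for a primary analysis. Still, the protocol itself fixes the Sensitivity 1 rule, and that rule is narrower than the analysis needs to be.

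**Conclusion.** The point holds for the primary analysis, Sensitivity 1 and Sensitivity 2. A patient still on drug without a Week 12 weekly mean is imputed under within-arm MAR in each. For Sensitivity 3 it holds only as a request for clarity: the plain wording shifts such gaps on CR845, and they would escape only if the primary-analysis split in Appendix 14.6 were carried over.

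The size cannot be fixed from the protocol. Under the assumed rates, equal missingness matters little (power 96% to 95% at 5% per arm), while 10% vs 5% lowers the difference from 20 to 16.5 points and power to 87%. These figures rest on the planning response rates, on MAR imputation returning those rates, and on an unadjusted test in place of the planned logistic model. They describe a sensitivity analysis. The primary analysis and the sample size are unaffected. This is a worthwhile, inexpensive improvement and not a flaw that undermines the trial.

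**What to change.** - **Sensitivity 1:** count as a nonresponder every patient without an observed Week 12 weekly mean, in addition to every patient who discontinues study drug early.
- **Sensitivity 3:** name the MNAR pattern and state that the shift applies to every imputed CR845 Week 12 value, whether or not the patient has stopped study drug. Make section 8.7.1 and Appendix 14.6 agree on this.

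The cost is about two sentences of text and no new data. The downside is a possibly less favourable sensitivity result.
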